Effect of Beetroot Extract Supplementation on the Athletic Performance of Trained Rugby Athletes

NCT07106489

Last version: January 15, 2025

Effect of Beetroot Extract Supplementation on the Athletic Performance of Trained Rugby Athletes.

Study Protocol:

- Objective:

To evaluate the effect of nitrate supplementation, based on the consumption of beetroot juice, on athletic performance in rugby players.

- Design:

The research use a quasi-experimental design, using a non-randomized, crossover controlled trial, with the aim of minimizing the effects associated with each athlete's individual performance patterns, given that each participant acted as their own control. A double-blind protocol was implemented. Participants were divided into two groups (Beetroot-Placebo and Placebo-Beetroot); the researcher prepared waffles containing both beetroot (a source of nitrates) and placebo. A person external to the study was responsible for administering the compounds to each group, ensuring the corresponding crossover was performed in the second phase of data collection, so that all participants received both the placebo and nitrate supplementation at the end of the study.

- Methods

Beetroot and placebo (Waffles):

These are given to participants on the third day before the physical tests, to be consumed from that day onward, the following day, and on the day of the physical tests. To ensure consumption of the compounds two hours before physical activity, participants must send a photo of their consumption with their sports practice schedule, and two hours before their appointment for the physical tests.

There is then a 3-day washout period, during which participants are not given any compounds and cannot consume foods rich in nitrates (they are given a list of these foods). The process is repeated with the crossover compound (those who received placebo receive beetroot, while those who received the placebo receive beetroot).

- Physical Tests:

The protocol implemented by Sella, F. et al. (2023) is followed, with the 40 meters sprint being the first test. Prior to performing the sprints, participants completed a 10-minute standardized warm-up comprising jogging, dynamic stretches, running drills, and three stride-outs at increasing intensity. The physical tests are then performed, beginning with a 40-meter sprint. After an adequate 10-minute rest period, the Bronco test is performed. After 20 minutes, strength tests are performed, starting with the squat and then the bench press, and ending with the Borg scale.

This protocol is followed on both testing days; participants perform tests on the same day of the following week, at the same time

- **Background**

Specifically, in the case of nitrates in rugby, the evidence is scarce. There are some studies, such as the one conducted by Esen et al. (2023), which evaluated the effect of beetroot supplementation on trained male rugby players. They were given an average of 12.8 mmol of nitrates and a placebo with less than 0.08 mmol of nitrates, ingested 3 hours before physical tests. These studies revealed no improvement in the yo-yo endurance test or the countermovement jump.

On the other hand, there is the study conducted by López-Samanes et al. (2022) on semi-professional female rugby players, which studied the influence of beetroot on neuromuscular performance. Providing similar amounts of nitrates to the aforementioned study yielded a positive response in the countermovement jump exercise; however, there were no differences in speed, agility, strength, and endurance tests. Thus, despite the dose, differences are found depending on the protocol used.

However, while specific studies on rugby are limited, there is research in sports or activities with similar characteristics. An example of this is the study by Domínguez et al. (2018), who evaluated the effect of beetroot supplementation on high-intensity intermittent exercise. Their research observed an improvement in performance when rest periods between efforts were short. These improvements were primarily attributed to increased resynthesis of phosphocreatine, which contributes to delaying its depletion. Increases in muscle power and speed were also reported, as well as a possible reduction in muscle fatigue, although the specific physiological pathway through which this response occurs is not yet fully understood.

In his study, Fernandes (2021) conducted a literature search on nutritional supplements that improve performance in elite soccer players, revealing the use of various supplements such as creatine, caffeine, sodium bicarbonate, beta-alanine, nitrates (from beetroot), among others. The results, focused on nitrates, reveal that 6 mmol of NO₃, used for at least 5 days, consumed 2 hours before training, improves soccer players' performance. Furthermore, they emphasize the importance of doubling the dose on game day. This study, compared to those presented initially,

highlights the need to find an appropriate protocol, including dosage and application time, for each specific sport. Although the trend for ball sports, according to these studies, implies the need for chronic, not just acute, intake, reflecting the need for further research in the field.

Delleli et al. (2023) conducted a systematic review of randomized controlled clinical trials evaluating the effect of beetroot supplementation on combat sports performance. They concluded that there was an improvement in different aspects of athletic performance, both with a single supplementation and multiple doses, in different combat sports; mainly oxidative metabolism in isometric and isokinetic exercises; however, there is variability in the results, associated with both individual factors and the characteristics of each individual sport. There are also other systematic reviews (Murphy et al. 2022 and Tan et al. 2022) that reflect the study of nitrates in sports, including team sports, with variability in their results. Therefore, the need for further research on the subject is evident, mainly in Colombia, where no results on the study of nitrates in rugby are found.

In addition, this supplement is endorsed by the Australian Institute of Sport (AIS) for use by classifying it in category A, due to its safety and level of scientific evidence (2022).

- Human subjects protection review board

Initially, the study was considered experimental and approved by the committee of the Faculty of Medicine of the National University of Colombia in minutes B.FM. 1. 002-CE-043-24. However, as the necessary sample of volunteers for randomization was not obtained (44 people were required, but 10 were obtained), the study was changed from experimental to quasi-experimental, and the changes were reviewed and approved by the same committee in minutes 2.FM. 1. 002- CE 105-25.

Bibliographic references:

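### The plan states a bar on nitrate-rich foods only for the 3-day washout, so it leaves dietary nitrate uncontrolled on the waffle and test days that form the beetroot-placebo contrast

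*Combined protocol and SAP*

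**What the plan says.** The Objective is "To evaluate the effect of nitrate supplementation, based on the consumption of beetroot juice", so the question is about nitrate. The product actually given is a waffle: under Design, "the researcher prepared waffles containing both beetroot (a source of nitrates) and placebo".

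Under Methods, Beetroot and placebo (Waffles), the product is handed out on the third day before testing, "to be consumed from that day onward, the following day, and on the day of the physical tests". Intake is checked by photograph: "participants must send a photo of their consumption with their sports practice schedule". These sentences contain no diet rule.

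The diet rule comes next and is tied to the washout: "There is then a 3-day washout period", "during which participants are not given any compounds and cannot consume foods rich in nitrates". Participants receive a list of the foods concerned. Then "The process is repeated with the crossover compound".

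Under Physical Tests, the two testing days are a week apart: "participants perform tests on the same day of the following week, at the same time". The ethics review section records that 10 volunteers were obtained where 44 were needed. The SAP analyses paired differences (beetroot minus placebo) by paired t-test or Wilcoxon test. For the t-test it defines the effect size as the mean difference over the standard deviation of the differences.

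**The concern.** The investigators evidently think dietary nitrate matters, since they hand out a food list. As written, though, the list applies on the days furthest from a test. In the days before each test, when nitrate intake forms the contrast, the plan does not say what athletes may eat.

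The quantity compared is then the waffle's nitrate plus whatever each athlete happened to eat in that block. Differences in diet between the two weeks go into the standard deviation of the paired differences, which is the denominator of both the t statistic and the SAP's effect size. With 10 athletes there is little precision to spare. Interpretation suffers too: after a null result, one could not tell an absent nitrate effect from a contrast diluted by nitrate-rich meals in the placebo block. No diet record or plasma or salivary nitrate measure is described that would settle it afterwards.

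**Working it through.** **Calendar.** Put test 1 on day 0 and test 2 on day 7 (Physical Tests). The washout follows test 1, so the bar covers days 1 to 3. The intake wording allows two readings.

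| Reading | Waffle days, block 1 | Waffle days, block 2 | Waffle days in total | Waffle days under the bar |
|---|---|---|---|---|
| Four-day blocks | -3 to 0 | 4 to 7 | 8 | 0 |
| Three-day blocks | -2 to 0 | 5 to 7 | 6 | 0 |

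From first waffle to test 2 there are 11 days (-3 to 7) or 10 days (-2 to 7), and the bar covers 3 of them. Reading the repeated process as including a second washout after block 2 adds no covered waffle day.

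**The plan's own figure.** The only design figure is the required sample of 44. It comes without an effect size, SD, power or sidedness, so it cannot be reproduced. Nothing below depends on it.

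**Size of the noise.** From the documents: n = 10 and a 95% confidence level, taken here as two-sided 5%. Assumed: response is linear in nitrate; an athlete's dietary nitrate is independent between blocks, with the same SD in each; and d is the true standardised paired effect with no dietary variation.

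Let the waffle difference be Δ, the response per unit nitrate b, the SD of the paired differences without dietary variation s, and the per-block dietary SD kΔ. Then:

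- d = bΔ / s
- variance of a paired difference = s² + 2b²k²Δ² = s²(1 + 2k²d²)
- attenuated effect d′ = d / √(1 + 2k²d²)

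The factor 2 arises because k is defined per block and each difference contains two blocks. Power is from the noncentral t distribution with 9 degrees of freedom.

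| True d | k | d′ | Power |
|---|---|---|---|
| 1.0 | 0 | 1.000 | 80.3% |
| 1.0 | 0.25 | 1/√1.125 = 0.943 | 75.6% |
| 1.0 | 0.5 | 1/√1.5 = 0.816 | 63.4% |
| 1.0 | 1.0 | 1/√3 = 0.577 | 37.2% |
| 0.5 | 0 | 0.500 | 29.3% |
| 0.5 | 0.25 | 0.5/√1.03125 = 0.492 | 28.6% |
| 0.5 | 0.5 | 0.5/√1.125 = 0.471 | 26.6% |
| 0.5 | 1.0 | 0.5/√1.5 = 0.408 | 21.2% |

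Neither d nor k is in the documents. The value d = 1.0 is used because it is about where 10 athletes give 80% power (exactly 80% at d = 0.996).

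**Days to add.** A list running from three days before the first waffle through test 2 covers days -6 to 7 (14 days) or -5 to 7 (13 days). Less the 3 already covered, that is 11 or 10 more days.

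**The case against.** **Silence is not permission.** A reader might infer that the list is lifted before each test, or that the placebo condition is not low in nitrate. The documents do not say so. They state no rule for those days and do not describe what was eaten. Staff may have applied the list more widely, and participant instructions may sit in consent pages that are not in this copy. This objection stands: the point concerns what the plan specifies, not what the athletes did.

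**The large power loss is near a worst case.** A reader might take the fall from 80% to 37% as the effect of the gap. It needs both a true d of 1.0 and a per-block dietary SD as large as the whole waffle difference. At d = 0.5 the same SD costs about 8 percentage points, and the sample of 10 limits power far more than diet does. This also stands, so both cases are shown.

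**Free diet is a legitimate setting.** Under blinding, diet should balance on average, and a free-diet comparison answers a practical question. That is right as far as it goes, and no fixed bias is claimed. But the Objective asks about nitrate, and a free-diet comparison answers that less cleanly.

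**Period imbalance.** One might infer that barring nitrate foods before block 2 but not before block 1 biases the pooled mean when the groups are unequal. The documents give neither group sizes nor any basis for the size of such a shift. Three or four days of unregulated diet before test 2 could also erase it. The argument applies to any period effect in a non-randomised crossover, so it is not relied on here.

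**Missing dose.** The nitrate content of each waffle and the number per day are not given, and the mmol figures in the Background belong to cited studies. On its own this is missing detail rather than a design fault. It matters here because dietary variation cannot be judged without the waffle difference.

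**Conclusion.** The point holds as a gap in the specification. The plan controls dietary nitrate on days 1 to 3 and states no control on any of the six or eight waffle days, including both test days, or before block 1. The consequence is added noise in the paired differences and a null result that is harder to attribute to nitrate; it is not a systematic shift in the mean.

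Under the linear, independent-diet model the loss of power with 10 athletes runs from negligible (29.3% to 28.6% at d = 0.5, k = 0.25) to large (80.3% to 37.2% at d = 1.0, k = 1.0). Where the trial lies in that range cannot be known without the waffle nitrate content and some measure of dietary variation. The calendar finding needs no assumption beyond the one-week interval and holds on both readings of the intake days. The change is worth making because it is cheap, not because the damage is shown to be large.

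**What to change.** **If the trial is still to run.** Apply the same food list, in both groups, to every waffle day and test day in both blocks, with the same 3-day lead-in before block 1 as before block 2. In practice the list runs from three days before the first waffle through test 2. The cost is 10 or 11 more days on a list the plan already provides, handed out earlier, with no extra visits, tests or participants. The drawbacks are more burden on athletes and a result that applies to athletes on a low-nitrate diet.

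**If data are already collected**, as the past tense of the ethics section and SAP suggests. Report on which days the list applied and the nitrate content of each waffle, from the recipe or an assay. If the list applied only in the washout, say so, word the conclusion as the effect of the beetroot waffle on a free diet, and do not read a null result as no effect of nitrate. The cost is a few lines of text, one recipe calculation or assay per waffle, and a narrower conclusion.

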A descriptive and exploratory analysis was performed on the collected data using the R program. Univariate tests were performed for the mean (paired Student t-test) or Wilcoxon depending on the type of variable (continuous or ordinal) and compliance with the assumptions of normality with a confidence level of 95%.

$$d = \frac{\bar{d}}{s_d}$$

Where:

\bar{d} = mean of the differences (Beetroot – Placebo)

s_d = standard deviation of the differences

Thus, for the Wilcoxon test, the following was used:

$$r = \frac{Z}{\sqrt{n}}$$

Where:

Z = Z statistics of the test

n = number of participants with data in both conditions

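### The SAP's paired tests ignore period in a two-sequence crossover: a shared week-to-week change inflates the SD of the differences and, if the sequence groups are unequal, biases the effect

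*Combined protocol and SAP*

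**What the plan says.** The protocol's Design section describes the study as "using a non-randomized, crossover controlled trial" and states: "Participants were divided into two groups (Beetroot-Placebo and Placebo-Beetroot". It gives no group sizes and does not require equal groups. Under Physical Tests, the whole battery is repeated once: "participants perform tests on the same day of the following week, at the same time". The ethics section reports the recruitment shortfall: "44 people were required, but 10 were obtained".

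The SAP introduces itself with "A descriptive and exploratory analysis was performed on the collected data" and names its tests in one sentence: "Univariate tests were performed for the mean (paired Student t-test) or Wilcoxon depending on the type of variable (continuous or ordinal". The confidence level is 95%. The effect size d divides the "mean of the differences (Beetroot – Placebo") by the SD of those same differences, over all athletes together. The Wilcoxon effect size r uses every athlete measured under both treatments. No period or sequence term appears in either document.

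**The concern.** A two-period crossover gives each athlete's treatment difference a period component whose sign depends on the order received. A one-sample test on pooled differences treats that component as noise, or as treatment effect if the orders are unequally represented. It is valid only if nothing systematic changes between the two test days, and the documents neither state nor justify that. Fixing weekday, hour, warm-up and test order limits some variation. It cannot rule out familiarisation with the tests, a change in training load, or fatigue.

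With near-equal groups, the stake is a missed or understated effect and an interval that is too wide. With a lopsided division, the stake is a biased estimate and false positives. With 10 athletes there is little precision to spare.

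**Working it through.** **Inputs from the documents.** N = 10; two sequences; test days a week apart; pooled differences; 95% confidence. The plan gives no period effect, SD, target effect or split, so it has no figure of its own to reproduce on this point. The 44 athletes originally required come without inputs, and nothing below depends on that number.

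**Assumptions.** Two-sided 5% test; normal differences with within-sequence SD σ = 1; τ = treatment effect; π = shared change from week 1 to week 2, in units of σ, taken as 0.25, 0.5 and 1; splits 5/5, 4/6, 3/7 and 2/8.

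**Step 1: expectations.** The treatment difference has mean τ − π in the Beetroot-first group (size nBP) and τ + π in the Placebo-first group (size nPB). Pooled:

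- E(mean difference) = τ + π(nPB − nBP)/N
- E(s_d²) = σ² + 4π²·nBP·nPB/[N(N − 1)]

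The second term is positive whenever both orders are used. At 5/5 the factor is 4·5·5/90 = 1.11, so with π = 1 the root-mean-square s_d is √2.11 = 1.45 and the bias is 0. At 2/8 the factor is 64/90 = 0.71, so with π = 1 it is √1.71 = 1.31 and the bias is 0.6 in absolute size.

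**Step 2: the planned paired t-test.** The mean difference is normal with variance 1/N. Independently, 9·s_d² is noncentral chi-square with 9 df and noncentrality 4·nBP·nPB·π²/N. Numerical integration gave the rates below; 200,000 simulated trials per cell agreed within 0.3 percentage points. Each cell is for π = 0.25 / 0.5 / 1.

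| Split | Absolute bias | Type I error | Power at τ = 1 |
|---|---|---|---|
| 5/5 | 0 / 0 / 0 | 4.4% / 3.0% / 0.7% | 78% / 72% / 48% |
| 4/6 | 0.05 / 0.10 / 0.20 | 4.6% / 3.7% / 1.7% | opposing bias: 74% / 63% / 29%; favouring: 82% / 81% / 70% |
| 3/7 | 0.10 / 0.20 / 0.40 | 5.3% / 6.1% / 6.4% | opposing bias: 70% / 53% / 16%; favouring: 86% / 88% / 87% |
| 2/8 | 0.15 / 0.30 / 0.60 | 6.6% / 10.6% / 20.1% | favouring bias: 89% / 93% / 97% |

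With π = 0, power is 80% at every split. Where bias favours the effect, part of the apparent power is the bias itself. Opposing-bias power at 2/8 was not calculated.

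**Step 3: interval and effect size.** At 5/5 and τ = 1, the mean 95% half-width is 0.72 / 0.79 / 1.02 (0.70 at π = 0). Mean d is 1.06 / 0.96 / 0.73 (1.09 at π = 0; the excess over 1 is the small-sample bias of d). In a lopsided split d can also rise: at 2/8 with π = 1 and favouring bias, the ratio of expectations is (1 + 0.6)/1.31 = 1.22, against 1.00.

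**Step 4: period-adjusted analysis.** Average the two sequence means and use the within-sequence SD on 8 df, with SE = 0.5·σ·√(1/nBP + 1/nPB). That is 0.316 at 5/5, equal to 1/√10, and 0.395 at 2/8. Type I error is 4.9–5.1% in every cell. Power at τ = 1 is 79%, 77%, 72% and 60% at 5/5, 4/6, 3/7 and 2/8, whatever π is.

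**Step 5: rank tests.** The signed-rank test behaves like the paired t-test. With π = 1, type I error is 0.6% and power 44% at 5/5, and type I error is 19% at 2/8. A rank-sum test comparing period differences between sequences does not depend on π; without ties its power is about 68%, 69%, 59% and 52% at the four splits. Signed-rank has 78% with π = 0; at 5/5 it has 70% with π = 0.5 and 44% with π = 1. At 2/8 the smallest possible two-sided rank-sum p is 2/C(10,2) = 2/45 = 0.044.

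**The case against.** The strongest objection is that the harm rests on inputs nobody has seen. The worst figures need a period shift of half an SD or more together with a lopsided split, and the protocol suggests neither. At 5/5 with π = 0.25 almost nothing is lost. Only a change shared across athletes matters, since athlete-specific change is already in σ, and the inflation holds on average, not in every data set. Test conditions are standardised and the analysis is called exploratory. At 5/5 and 4/6 the paired test is conservative, so a positive result there would not be undermined.

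Nor is adjustment always better. With unequal groups the paired estimate has the smaller mean squared error when π² < N/(4·nBP·nPB), that is π below 0.32 (4/6), 0.35 (3/7) or 0.40 (2/8). At 2/8 with π = 0.25 the values are 0.1 + 0.15² = 0.1225 for the paired estimate and 0.25·(1/2 + 1/8) = 0.156 for the adjusted one. At 5/5 the two point estimates are identical.

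All of this stands as a limit on size and as a reason to show both analyses. It does not supply the missing assumption. A lopsided split is not shown, but equal groups are not shown either, and even equal enrolment could become unequal among athletes with both measurements. The SAP still reports tests, 95% confidence and effect sizes, and its pooled analysis gives no estimate of the period change.

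**Conclusion.** The concern holds. The planned analysis omits period from a two-sequence crossover. In expectation, any shared week-to-week change inflates s_d at every split; it also biases the treatment effect when the sequence groups differ in size. If there is no such change, the paired test is valid.

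The size cannot be fixed from the documents. Over the assumed range it runs from negligible (5/5, π = 0.25) to a loss of 32 points of power (5/5, π = 1: 80% to 48%) or a type I error of 20.1% (2/8, π = 1). Near balance the main risk is a missed or understated effect; false positives become the problem only as the split grows lopsided. The algebra is certain; the split and π are assumptions. This should be fixed because the omission is clear and the repair needs no new data.

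**What to change.** 1. Report the number of athletes in each sequence, both enrolled and analysed.
2. For continuous outcomes, fit a linear model with treatment, period and athlete effects. Equivalently, compare within-athlete period differences between the two sequences with a two-sample t-test and halve the contrast.
3. For the Borg scale and clearly non-normal outcomes, use a rank-sum test on the period differences.
4. Report the treatment effect with its 95% CI, the period estimate, and a standardised effect based on the period-adjusted SD.
5. Show the adjusted result beside the paired one. The SAP is written in the past tense, so label the adjusted analysis as added later if the data have been seen.
6. State its limits. It assumes the same period change in both non-randomised groups; a gap of δ between them biases the estimate by δ/2. It does not remove carryover; beetroot carryover of λ into the placebo week biases it by −λ/2.

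The cost is SAP wording and a few lines of R. Each athlete's order must already be recorded, since a treatment difference cannot be formed without it. The model uses one degree of freedom (8 instead of 9). With no period effect, the power cost at τ = 1 is about 1 point at 5/5, 3 at 4/6, 8 at 3/7 and 20 at 2/8. The rank version costs more, about 10 points at 5/5 (68% against 78%), and at 2/8 it can barely reach significance.

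### Does testing five performance measures, with no primary outcome or multiplicity control, call for a change to the SAP?

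*Combined protocol and SAP*

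**What the plan says.** The Objective section of the protocol sets one broad aim: "To evaluate the effect of nitrate supplementation, based on the consumption of beetroot juice, on athletic performance in rugby players". The Physical Tests section describes a session with five measures. The 40-metre sprint comes first. Next, "After an adequate 10-minute rest period, the Bronco test is performed". The session then closes with strength tests and a rating scale: "After 20 minutes, strength tests are performed, starting with the squat and then the bench press, and ending with the Borg scale".

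The SAP is one short section. It opens: "A descriptive and exploratory analysis was performed on the collected data using the R program". It continues: "Univariate tests were performed for the mean (paired Student t-test) or Wilcoxon depending on the type of variable (continuous or ordinal"), with the choice of test also resting on "compliance with the assumptions of normality with a confidence level of 95" percent. Two effect sizes follow: the mean difference over the SD of the differences for the t-test, and Z over the square root of n for Wilcoxon, where n is the "number of participants with data in both conditions".

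The section on the human subjects review board records the recruitment shortfall: "44 people were required, but 10 were obtained".

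Neither the protocol nor the SAP names a primary outcome, defines a successful result, adjusts for multiple tests, lists the variables tested or says whether tests are two-sided.

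**The concern.** Five measures serve a single question, and each appears to be tested at the usual level with no hierarchy among them. In a plan of that shape, any one of five significant results could be presented as evidence that beetroot improves performance, and the chance that at least one arises by luck exceeds the nominal rate for a single test. In a trial of 10 people that set out to recruit 44, a lone significant result would be easy to over-read. The SAP's silence on a primary outcome and on how a mixed set of results should be read therefore looks like a gap to be closed.

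**Working it through.** The documents state no familywise error rate, so there is no plan figure to reproduce. The 44 cannot be checked either, because no effect size, SD, power or outcome is given for it. The check asks how large the inflation could be, and what removing it would cost.

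**Inputs from the documents.** Five measures (Physical Tests); 95% confidence, read as 5% per test (SAP); n = 10 (review board section).

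**Assumptions, because the documents are silent.** All five measures are tested, each once. Tests are two-sided, giving 2.5% in the direction of improvement. Each outcome is signed so that positive means better. There is no true effect, and the paired tests are otherwise valid. The beetroot-minus-placebo differences share a common correlation ρ.

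**Independent outcomes (ρ = 0).**
- Five tests, at least one false improvement: 1 − 0.975^5 = 0.119.
- Four tests (without Borg): 1 − 0.975^4 = 0.096.
- Five tests, either direction: 1 − 0.95^5 = 0.226.

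**Correlated outcomes.** Simulation of five paired t-tests at n = 10 with equicorrelated normal differences (400,000 replicates):

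| ρ | False improvement, five tests | Either direction, five tests | False improvement, four tests |
|---|---|---|---|
| 0 | 11.9% | 22.7% | 9.7% |
| 0.5 | 9.6% | 19.2% | 8.0% |
| 0.7 | 7.9% | 15.8% | 6.9% |
| 0.9 | 5.4% | 10.9% | 4.9% |

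The single-test comparators are 2.5% and 5%. Replacing one t-test by an exact Wilcoxon test changes almost nothing (11.8% at ρ = 0 and 5.5% at ρ = 0.9 for improvement). Above 0.9 the false-improvement rate keeps falling, to about 4.5% at 0.95 and 3.7% at 0.98, with a limit of 2.5% at perfect correlation. The 5% end of the range therefore reflects where the assumed correlation stops. It is not a floor.

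**Cost of adjusting.** The first Holm step for five outcomes tests at 0.05/5 = 0.01. Power of a two-sided paired t-test from the noncentral t distribution:

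| n | True effect (SD of differences) | Power at 0.05 | Power at 0.01 |
|---|---|---|---|
| 10 | 1.0 | 80.3% | 50.4% |
| 10 | 0.5 | 29.3% | 10.3% |
| 8 | 1.0 | 68.1% | 34.8% |

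If all five outcomes had a 1 SD effect, Holm's later steps would bring per-outcome power back to about 60% to 65%. For an exact two-sided Wilcoxon test with m untied non-zero pairs, the smallest possible p is 2/2^m: 0.0078 at m = 8 and 0.0156 at m = 7. With seven or fewer such pairs the first Holm step cannot be passed whatever the data show.

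**What adjustment would not address.** The calculations assume tests free of bias, while the Design and Methods sections describe non-randomized sequences and a 3-day washout. As an illustration (assumed figure), a net bias of 0.3 SD of the differences gives a single test at n = 10 a 13.4% false-improvement rate, above the whole multiplicity range. Holm's nominal control would not hold under such a bias.

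**The case for a change.** The strongest case for a change is that an exploratory label does not tell the reader how five tests of one objective are to be interpreted. The SAP still specifies tests at 95%, so significant and non-significant labels will be produced. The protocol's own Background cites a women's rugby study with a positive jump result and no differences in speed, agility, strength or endurance, which is the kind of mixed pattern this plan has no rule for. The remedy would be cheap: list the outcomes, state that tests are two-sided, report every estimate with its interval, add Holm-adjusted p-values, and say that no claim rests on one unadjusted p-value. The SAP's past tense is no obstacle, since none of this needs new data.

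Part of that stands. The omissions are real, the inflation is correctly calculated under its assumptions, and a report that gave all outcomes with intervals and repeated the exploratory limit would be better for it. That is good reporting practice, and a competent analyst would do it without an amended plan. It does not show that a stated rule or figure is wrong. The Holm component is a matter of judgement on which reasonable statisticians would differ, and, if the analysis has already been run, an adjustment chosen now would be post hoc. The remedy also supplies neither the primary outcome nor the success rule whose absence prompted the concern. Counting Borg as a fifth performance outcome is an inference too: the Physical Tests section says only that the session ends with it, although the SAP's mention of ordinal variables fits its being tested.

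**Conclusion.** The concern does not lead to a change. Under two-sided 5% tests of all five measures, no true effect, valid tests and a correlation from 0 to 0.9, the chance of at least one false improvement is about 12% down to 5%, against 2.5% for one test. Without Borg it is about 10% down to 5%, and it falls toward 2.5% as the correlation rises above 0.9. The correlation, the sidedness and the set of variables tested are all assumed.

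That inflation would matter if the plan let one significant test carry a conclusion, and it contains no such rule. The SAP declares itself descriptive and exploratory and pairs each type of test with an effect size. Formal error control is a choice in that setting, and here it is an expensive one: with 10 of 44 participants, missed effects are at least as serious a worry as false ones. The unlisted variables and unstated sidedness are gaps that ordinary practice fills. Leaving the tests unadjusted under an exploratory label is a fair trade-off.
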